Accrual Period	Up to 2 years
Study Design	This study is a prospective observational cohort study of TB
	patients who are treated or evaluated at 10 study sites.
	Patients presenting with cough for 2 weeks or longer with at
	least one additional TB symptom and a chest X-ray suggestive
	of TB, will be invited to be enrolled in the study. The signed
	informed consent will designate their willingness to participate
	on this study. Enrolled participants will produce the sputum
	for bacteriological examination of M. tuberculosis by AFB,
	culture and Xpert. The sputum will also be tested by Xpert
	for drug resistance test. If the culture is positive, conventional
	DST will be performed, and M. tuberculosis isolates will be
	stored for spoligotyping and for future research on TB. All
	participants treated by TB drugs regimen will be followed for
	outcome assessment. For all enrolled participants, chest X-Ray
	results, demographic data, co-morbidities, symptoms, nutritional
	status, treatment regimens, compliance and outcome will be
	collected. In addition, sputum, blood, urine, and saliva will also
	be collected for related TB future testing.

Primary Objective	To estimate the proportion of MDR-TB amongst new and
	previously treated TB cases.
Secondary Objectives	
	j. Treatment regimens

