4.4 Population and Sample Size

This is a descriptive study with the goal of estimating rates MDR in two separate cohorts (new and previously treated TB cases). WHO global report in 2013 estimated 1.9% MDR TB cases in new TB cases and 12% MDR TB cases in previously treated TB cases for Indonesia. This study will analyze 250 bacteriologically confirmed new TB participants and 250 bacteriologically confirmed previously treated participants. We estimate that 25% of presumptive new TB participants who satisfy study entry criteria will be bacteriologically confirmed TB. Similarly, we estimate that 70% of previously treated cases will be bacteriologically confirmed TB. Therefore, to obtain 500 bacteriologically confirmed TB cases and 357 presumptive previously treated cases will be enrolled, for a total of 1,357 enrolled. The proportion of confirmed TB cases amongst new and previously treated cases is an estimation and will be re-evaluated during the course of the study. Refer to the interim analysis section below for details.

Table 4.4.1 describes the expected precision (confidence bounds and width) for observed proportion of MDR amongst previously treated cases. With 250 participants and an observed MDR proportion of 12%, the confidence interval will be (0.085, 0.162). The precision of the estimated proportion of MDR does not improve considerably when increasing the sample size to 300. The confidence interval for a sample size of 300 with an MDR proportion of 12% is (0.085, 0.162), while decreasing the sample size to 200 has a more striking impact on the bounds increasing the lower bound to 0.078 and the upper bound to 0.173.

When considering the sample size for new TB cases, we note that the precision of binomial confidence intervals based on exact Clopper Pearson method increases as the proportion gets closer to zero. As a result, we find the true MDR rate is more precisely estimated with a sample size of 250 for new TB cases (compared to previously treated cases, where the MDR rate is expected to be around 12%). With a sample size of 250

new TB cases, the expected 95% confidence interval is (0.007, 0.046). (Table 4.4.1) Exact Clopper Pearson binomial confidence interval method formula:

$$\left(1 + \frac{n - x + 1}{xF\left[1 - \frac{1}{2}\alpha; 2x, 2(n - x + 1)\right]}\right)^{-1} < \theta < \left(1 + \frac{n - x}{[x + 1]F\left[\frac{\alpha}{2}; 2(x + 1), 2(n - x)\right]}\right)^{-1}$$

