4.6 Instruments and Data Collection'

The following instruments and data collection methods will be used in this study. Further information may be found in protocol sections 4.6.2-4.6.5.

- 4.6.1 Instruments:
 - a. Forms
 - i. Informed consent
 - ii. Source documents
 - iii. Case report forms (CRFs)
 - iv. Screening Log
 - v. Enrollment Log
 - b. Databases
 - i. OpenClinica

ii. INA-RESPOND specimen database

- c. INA-RESPOND portal
- 4.6.2 Eligibility determination and enrollment:

Enrollment and baseline visit (visit 1)

Potential participants will be referred by physicians at participating hospitals.

Following referral, research assistant will check the eligibility criteria. Thus, the potential participant will be offered information on the study. If the patient agrees, he/she will sign the informed consent document and will be considered enrolled in the study. All baseline procedures should be done in five working days, although the result may come later. Enrollment day is considered as Day 0.

Demography, clinical data, and physical examination results including body weight and height will be obtained. The initial data collection will take time about 30-60 minutes.

Participant should bring enough sputum that can be considered eligible for AFB, Xpert MTB/RIF, and culture examination. Sputum induction by inhalation medicine will be considered for participants that have difficulty to produce sputum according to site SoC. The remaining sputum will be stored for TB related future testing. Participant who cannot provide enough sputum for those examinations will be considered as end of study and stop following the study procedures.

20 cc blood will be drawn for assessment of comorbidities (HIV test and HbA1c), for other examinations needed either for study or for SoC. Such as Hb, ureum, creatinine, AST, and ALT. Left over specimen will be used for future TB related examinations and repository. Less blood volume because unanticipated problem related to blood draw such as collapsing vein would not be considered as protocol deviation. 10 cc of urine will also be collected and stored for future TB related tests. Saliva will also be collected for storage.

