After the sputum culture shows positive results of M.*tuberculosis*, the *M.tuberculosis* isolate will be tested for DST and also be stored. New TB cases with Rif susceptible Xpert MTB/RIF result will be tested for first line DST, continue by second line if first line DST result shows drug resistant TB. New TB cases with Rif resistant Xpert MTB/RIF will be directly tested for first and second line DST. Previously treated TB cases will be directly tested for first and second line DST.

DS-TB participants who decide to take the TB treatment in puskesmas (primary health care) may not come to visit(s) except for study visit which the study gives compensation for participant's attendance. So that for those participants, study will provide a record, named "TRIPOD Diary", to be completed on each visit at Puskesmas. The TB program manager or designee at the Puskesmas will give their signed as a verification of this record. TRIPOD Diary will be mentioned further in MOP.

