SoC	: Procedure must be done regularly on site

IA : Procedure might be done on site for all or some groups of participants

All available data must be recorded for study

Variables	Measurement	Operational definition
New TB cases	Patient report	TB patients who never have TB treatment or already have TB treatment less than one month (4 weeks)
Previously treated TB cases	Patient report	A patient who has been treated for one month or more with anti TB drugs in the past
Presumptive TB	Clinical and X-Ray evaluation	Patient who presents with symptoms or signs suggestive of TB on the basis of X-ray suggestive TB
Bacteriologically confirmed TB	Laboratory evaluation	A participant whom a biological specimen is positive by AFB or culture or WRD (such as Xpert MTB/RIF)
Clinically diagnosed TB	Clinical and X-Ray evaluation	Participant who does not fulfil the criteria for bacteriological confirmation but has been diagnosed with active TB by a clinician or other medical practitioner who has decided to give the patient a full course of TB treatment, includes cases diagnosed on the basis of X-ray abnormalities
Pulmonary TB	Clinician judgement	Any bacteriologically confirmed or clinically TB involving the lung parenchyma or the tracheobronchial tree, including miliary TB, patient with both pulmonary and extrapulmonary TB should be classified as a case of PTB.
Extrapulmonary TB	Clinician judgement	Any bacteriologically confirmed or clinically diagnosed case of TB involving organs other than the lungs, e.g. pleura, lymph nodes, abdomen, genitourinary tract, skin, joints
Drug Sensitive/susceptible TB	By the result of Drug susceptibility test (DST)	Negative DST result
MDR TB	By the result of Drug susceptibility test (DST)	DST result positive resistant to isoniazid and rifampicin
Rif Resistance TB	By the result of Drug susceptibility test (DST)	DST result positive resistant to rifampicin

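### The primary MDR proportion is sized on 250 confirmed cases per group, but MDR status needs a DST result; no DST yield is allowed for and section 4.7.2 does not name the denominator

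*Combined protocol and SAP*

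**What the plan says.** Section 4.4 sets the sample size for the primary objective: "This study will analyze 250 bacteriologically confirmed new TB participants and 250 bacteriologically confirmed previously treated participants". It assumes that 25% of presumptive new cases and 70% of presumptive previously treated cases will be confirmed, and recruitment stops at 1,000 and 357. Tables 4.4.1 and 4.4.2 give exact 95% intervals by sample size.

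Appendix B defines a bacteriologically confirmed case as "A participant whom a biological specimen is positive by AFB or culture or WRD (such as Xpert MTB/RIF"), so a positive culture is not required. The same appendix defines MDR TB as "DST result positive resistant to isoniazid and rifampicin" and drug-susceptible TB as "Negative DST result".

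The study design in the Research Summary makes conventional DST conditional: "If the culture is positive, conventional" DST follows. Section 4.6.2 agrees: once culture is positive, the "isolate will be tested for DST and also be stored". On specimens, 4.6.2 adds: "Participant who cannot provide enough sputum for those examinations will be considered as end of study".

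Section 4.7.2 promises exact binomial 95% intervals for the MDR proportion in new and retreated cases and refers to Appendix B for the case definitions. It does not say which participants form the denominator. It defers more specific analysis plans to a later step before enrolment and allows them to be adjusted during the study. The checks at 6 and 12 months look at the 25% and 70% confirmation estimates.

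**The concern.** The sample size counts one unit and the endpoint is defined on another. A participant who is positive by AFB or Xpert, but whose culture is negative or whose DST gives no usable result, counts towards the 250 and yet is neither MDR nor drug-susceptible under Appendix B. Xpert cannot fill the gap: the plan uses it for rifampicin only, and evaluates it against DST as the reference.

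Two things follow for the study's only primary objective. First, the n = 250 intervals are more favourable than the design is expected to deliver once some confirmed cases lack DST. Second, the point estimate depends on what is done with untested cases, and 4.7.2 does not settle this. Dropping them and keeping them as non-MDR give different proportions from the same data.

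**Working it through.** **Inputs from the documents.** Target 250 per group, yields 25% and 70%, caps 1,000 and 357 (section 4.4). Anticipated MDR 12% in previously treated cases; 2% is the row of Table 4.4.2 closest to the 1.9% quoted for new cases. Exact (Clopper-Pearson) two-sided 95% intervals.

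**Input not in the documents.** The DST yield f, meaning the share of confirmed cases with a valid DST result. It is an assumption, shown here at 95%, 90% and 80%.

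**Step 1: reproduce the plan.** Enrolment: 250/0.25 = 1,000 and 250/0.70 = 357.1, total 1,357. In reverse, 1,000 × 0.25 = 250 and 357 × 0.70 = 249.9, so the caps hold no reserve.

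Interval: lower limit = the 0.025 quantile of Beta(x, n − x + 1); upper limit = the 0.975 quantile of Beta(x + 1, n − x), with x = n × p (fractional where needed, which matches the tables).
- 30/250: (0.0824, 0.1669), width 0.0844. Table 4.4.1 gives (0.082, 0.167), 0.084.
- 5/250: (0.0065, 0.0461), width 0.0395. Table 4.4.2 gives (0.007, 0.046), 0.040.

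Both tables reproduce. The running text of 4.4 prints (0.085, 0.162) for n = 250 at 12%. That is the n = 300 row (36/300), so the table values are used here.

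**Step 2: expected evaluable n and precision.** n = 250 × f.

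| f | n | 95% CI at 12% | Width | 95% CI at 2% | Width |
|---|---|---|---|---|---|
| 100% | 250 | (0.082, 0.167) | 0.0844 | (0.007, 0.046) | 0.0395 |
| 95% | 237.5 | (0.082, 0.168) | 0.0867 | (0.006, 0.047) | 0.0407 |
| 90% | 225 | (0.081, 0.170) | 0.0892 | (0.006, 0.048) | 0.0420 |
| 80% | 200 | (0.078, 0.173) | 0.0949 | (0.005, 0.050) | 0.0449 |

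Relative widening at 12%: 0.0867/0.0844 = 1.03, 0.0892/0.0844 = 1.06, 0.0949/0.0844 = 1.12. At 2%: 0.0407/0.0395 = 1.03, 0.0420/0.0395 = 1.06, 0.0449/0.0395 = 1.14.

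**Step 3: effect of the denominator.** Suppose untested cases have the same MDR risk p as tested ones. The DST-tested denominator gives p. Keeping untested cases as non-MDR gives f × p:
- 12%: 0.95 × 12 = 11.4%, 0.90 × 12 = 10.8%, 0.80 × 12 = 9.6%.
- 2% at 90% yield: 0.90 × 2 = 1.8%.

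**Step 4: what the DST-tested denominator assumes.** Let untested cases have relative risk r, with true overall p = 12%. The DST-only proportion is p/(f + (1 − f)r). With f = 0.90 and r = 0.5 it is 0.12/0.95 = 12.6%, and keeping untested cases as non-MDR gives 0.90 × 12.6 = 11.4%. Neither is unbiased, so the DST-only estimate relies on similar risk in untested cases.

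**The case against.** The strongest reply is that this is small and perhaps already handled.

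- **Size.** At 90-95% DST yield the intervals widen by 3-6%. The study is descriptive, with no test on the primary objective and no required width, and the tables already print n = 200 and n = 150. This stands, and it limits the weight of the point.
- **Yield is unknown.** This also stands. Only a range can be shown, and the loss could be near zero.
- **Safeguards.** Participants without enough sputum for all three examinations leave the study, and the 6- and 12-month checks are timed with the wait for culture in mind. The first secures a specimen, not a positive culture or a valid DST. The second tracks confirmation yields, which could be met exactly while DST results fall short.
- **Later plans.** More specific plans may name the denominator. They are not in the documents, and they may change during the study. Figure 1 is not shown in the text available.

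Some stronger readings are tempting but not supported:
- A reader might infer that 250 is a ceiling that the study cannot reach. It is an expected value. For example, confirmation yields of 27.5% and 75% with 95% DST yield would give 1,000 × 0.275 × 0.95 = 261 and 357 × 0.75 × 0.95 = 254. The plan also sets no criterion that 250 must be reached, so the chance of reaching it measures no failure.
- A reader might infer that the plan counts untested cases as non-MDR. No section says so. Section 4.7.2 points to Appendix B, where an untested case belongs to neither class, which makes that reading the less likely one.
- A reader might take 4.4's remark on dropping to 200 as its own admission of a serious loss. That paragraph sets n = 200 against the misprinted n = 250 interval, implying a widening from 0.077 to 0.095 instead of 0.084 to 0.095.

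**Conclusion.** The mismatch is real and concerns the primary objective. Section 4.4 states its size and precision on confirmed cases, while the endpoint exists only for cases with DST. At the planned yields and caps, the two coincide in expectation only at 100% DST yield.

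The precision loss is small at 90-95% yield and moderate at 80% (12-14% wider). The open denominator matters more, because it moves the estimate itself: 12% against 10.8% at 90% yield under equal risk. Appendix B points to the DST-tested denominator, so the downward bias arises only if the wording of 4.4 is applied literally and some untested cases have MDR.

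Confidence is high that the text leaves this gap. The size of the effect rests on a DST yield, and on the MDR risk in untested cases, that the documents do not give. The point should be fixed, mainly by wording.

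**What to change.** 1. In sections 4.4 and 4.7.2, define the primary denominator, separately for new and previously treated cases, as confirmed participants with valid isoniazid and rifampicin DST results.
2. In 4.4, state an assumed DST yield and restate the expected evaluable n and exact interval under it, keeping the 1,000 and 357 caps.
3. Add the DST-evaluable count per group to the 6- and 12-month checks.
4. Report, per group, the confirmed cases without DST together with their Xpert rifampicin result. State that the DST-only estimate assumes similar MDR risk in untested cases.

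The cost is protocol and SAP wording, one extra table row per group and one more count at checks already planned; no patients or procedures are added. The downside is that the stated precision becomes slightly less favourable and is not recovered. The similar-risk assumption can be checked only in part, since Xpert informs on rifampicin but not isoniazid.

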Table 4.4. 1 Expected confidence bounds based on observed MDR proportions amongst previously treated TB cases.

Sample Size	Observed proportion	Bounds of 95% confidence interval*	Actual width
150	0.12	(0.073, 0.183)	0.110
	0.15	(0.097, 0.217)	0.120
200	0.12	(0.078, 0.173)	0.095
	0.15	(0.104, 0.207)	0.104
250	0.12	(0.082, 0.167)	0.084
	0.15	(0.108, 0.200)	0.092
300	0.12	(0.085, 0.162)	0.077
	0.15	(0.112, 0.196)	0.084
400	0.12	(0.090, 0.156)	0.066
	0.15	(0.116, 0.189)	0.072

* Cls based on Exact Clopper-Pearson method

Table 4.4. 2 Expected confidence bounds based on observed MDR proportions amongst new TB cases.

Sample size	Observed proportion	Bounds of 95% confidence interval*	Actual width
150	0.01	(0.001, 0.042)	0.041
	0.02	(0.004, 0.057)	0.053
	0.03	(0.009, 0.072)	0.062
	0.05	(0.021, 0.098)	0.077
200	0.01	(0.001, 0.036)	0.034
	0.02	(0.005, 0.050)	0.045
	0.03	(0.011, 0.064)	0.053
	0.05	(0.024, 0.090)	0.066
250	0.01	(0.002, 0.032)	0.030
	0.02	(0.007, 0.046)	0.040
	0.03	(0.013, 0.059)	0.047
	0.05	(0.027, 0.085)	0.058
300	0.01	(0.002, 0.029)	0.027
	0.02	(0.007, 0.043)	0.036
	0.03	(0.014, 0.056)	0.042
	0.05	(0.028, 0.081)	0.053

400	0.01	(0.003, 0.025)	0.023
	0.02	(0.009, 0.039)	0.03
	0.03	(0.016, 0.052)	0.036
	0.05	(0.031, 0.076)	0.045

* CIs based on Exact Clopper-Pearson method

The sampling method in this study is purposive sampling. The study will stop recruiting participants when 1,000 new presumptive TB cases and 357 previously treated TB cases had enrolled.

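### Section 4.4 states the n = 300 confidence interval as the precision for the planned 250 previously treated cases, contradicting Table 4.4.1

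*Combined protocol and SAP*

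**What the plan says.** Section 4.4 plans "250 bacteriologically confirmed previously treated participants" and takes as background a WHO estimate of "12% MDR TB cases in previously treated TB cases for Indonesia". It sets out no hypothesis test and supports the sample size by expected confidence-interval precision.

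For previously treated cases the text makes four statements:

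- At the planned size: "With 250 participants and an observed MDR proportion of 12%, the confidence interval will be (0.085, 0.162").
- On enlarging the cohort: "The precision of the estimated proportion of MDR does not improve considerably when increasing the sample size to 300".
- In support of that: "The confidence interval for a sample size of 300 with an MDR proportion of 12% is (0.085, 0.162").
- On shrinking it: "decreasing the sample size to 200 has a more striking impact on the bounds increasing the lower bound to 0.078", with the upper bound going to 0.173.

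For new cases it says: "new TB cases, the expected 95% confidence interval is (0.007, 0.046). (Table 4.4.1").

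Table 4.4.1, which the text introduces as the source for previously treated cases, lists at an observed proportion of 0.12:

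| n | 95% interval | Width |
|---|---|---|
| 200 | (0.078, 0.173) | 0.095 |
| 250 | (0.082, 0.167) | 0.084 |
| 300 | (0.085, 0.162) | 0.077 |

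The interval (0.007, 0.046) for new cases is in Table 4.4.2 ("Expected confidence bounds based on observed MDR proportions amongst new TB cases"), in the row for n = 250 and proportion 0.02.

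**The concern.** At a fixed observed proportion, an exact binomial interval narrows as n grows. Sample sizes of 250 and 300 at 12% cannot share an interval to three decimals, so at least one of the two sentences has to be wrong.

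The location gives the slip some weight. Precision is the only quantitative support offered for the sample size, and this sentence states it for a primary-objective cohort at the size actually chosen. The argument for 250 then rests on comparing it with 300 and 200. If the 250 entry is really the 300 entry, the upward comparison sets an interval against itself and shows no gain, while the downward comparison starts from an interval that is too narrow and shows too large a loss. Both distortions favour 250. A report that took its planned precision from the text would carry the wrong figure forward.

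**Working it through.** **Inputs.** Two-sided 95%, exact Clopper-Pearson (section 4.4 and its table footnotes; section 4.7.2, Analysis). An observed 12% gives x = 24 of 200, 30 of 250 and 36 of 300.

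**Formula.** As printed in section 4.4, with F read as the quantile giving the usual equal-tailed interval:

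- Lower = 1 / (1 + (n − x + 1) / (x·F_L)), where F_L is the 2.5th percentile of F with 2x and 2(n − x + 1) degrees of freedom.
- Upper = 1 / (1 + (n − x) / ((x + 1)·F_U)), where F_U is the 97.5th percentile of F with 2(x + 1) and 2(n − x) degrees of freedom.

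**Step 1: the planned size, 30 of 250.**

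- Lower: F_L (60, 442 df) = 0.6619, so 1 / (1 + 221 / (30 × 0.6619)) = 0.0824.
- Upper: F_U (62, 440 df) = 1.4213, so 1 / (1 + 220 / (31 × 1.4213)) = 0.1669.
- Width 0.0844.

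This is the n = 250 row of Table 4.4.1. It is not the interval in the text.

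**Step 2: the three sizes compared in the text.**

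| x / n | Recomputed | Width | Table 4.4.1 | Text |
|---|---|---|---|---|
| 24 / 200 | (0.0784, 0.1733) | 0.0949 | (0.078, 0.173) | (0.078, 0.173) |
| 30 / 250 | (0.0824, 0.1669) | 0.0844 | (0.082, 0.167) | (0.085, 0.162) |
| 36 / 300 | (0.0855, 0.1622) | 0.0768 | (0.085, 0.162) | (0.085, 0.162) |

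The text fails only at n = 250. The lower bound is off by 0.085 − 0.082 = 0.003 and the upper by 0.167 − 0.162 = 0.005, both in the favourable direction.

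**Step 3: could another method or count explain the printed interval?** For 30 of 250 at 95%: Wald (0.080, 0.160), Wald with continuity correction (0.078, 0.162), Wilson (0.085, 0.166), Agresti-Coull (0.085, 0.167), Jeffreys (0.084, 0.165). None matches. Nor do the 90% and 97.5% levels (tried without the continuity correction), or Clopper-Pearson with 28, 29 or 31 events. Searching n from 200 to 399 at 12%, (0.085, 0.162) arises only for n = 297 to 300. All 30 rows of Tables 4.4.1 and 4.4.2 reproduce to rounding, so the fault is in the text.

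**Step 4: effect on the comparison.**

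| Change from 250 | As the text prints it | Correct (unrounded widths) |
|---|---|---|
| to 300 | 0.077 to 0.077: 0% | 0.0844 to 0.0768: −0.0076, about 9% narrower |
| to 200 | 0.095 / 0.077 − 1: 23% wider | 0.0949 / 0.0844 − 1: +0.0104, about 12% wider |

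**Step 5: the other two slips.**

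- At n = 200 the lower bound is 0.078. That is below both the correct 0.082 and the misprinted 0.085 for n = 250, so it decreases.
- 5 of 250 (2%) gives (0.0065, 0.0461), which rounds to (0.007, 0.046). The new-case interval is right, but it belongs to Table 4.4.2, and the sentence does not state the 2% behind it.

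**The case against.** The strongest reply is that this is a copying slip with no consequence. The correct interval is printed in the table that the paragraph cites. The bounds are off by at most half a percentage point. Section 4.4 sets no target width, so no criterion is missed at 0.084 rather than 0.077. The primary analysis computes exact intervals from observed data, and neither the enrolment targets of 1,000 and 357 nor the 6- and 12-month checks of the confirmation rates use this interval. The qualitative argument also survives: losing 50 participants still costs more precision (0.0104) than gaining 50 buys (0.0076), and whether a 9% narrowing is considerable is a matter of judgement. Finally, the text prints bounds only, so the 0% and 23% figures are derived from it rather than stated in it.

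Most of this stands, and it limits the finding to a correction of text. It does not make the sentence right. The sentence contradicts its own source on the expected precision of a primary-objective cohort, in the favourable direction, and the comparison built on it shows no gain at 300 where there is one. A reader should not need the table to discover that the text is wrong.

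Eight rows of the two tables (n = 150 and 250 at 0.01, 0.03, 0.05 and 0.15) use fractional event counts that could not be observed, for example 37.5 of 250. None of the intervals discussed here comes from those rows.

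**Conclusion.** The concern holds. The interval stated in the text for 250 previously treated cases at 12% MDR is the n = 300 interval. The correct one is (0.082, 0.167), width 0.084, so the text understates the width by about 9% and credits the planned cohort with the precision of one 50 confirmed cases larger. The contrast between 200, 250 and 300 is much weaker than printed, though its ordering is unchanged. The reversed direction for the lower bound and the wrong table reference are separate, smaller errors.

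The conclusion rests only on the method, confidence level, sample sizes and proportion stated in the protocol. It does not call the sample size of 250 into question, and no analysis changes. It should be fixed because it concerns the stated precision for the primary objective.

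**What to change.** Amend the text of section 4.4 in three places:

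1. Give the interval for 250 participants at 12% as (0.082, 0.167), width 0.084. Restate the comparison with all three widths: 0.077 at 300, about 9% narrower than at 250, and 0.095 at 200, about 12% wider. These percentages come from unrounded widths; the rounded table widths give 8% and 13%.
2. For 200 participants, say that the lower bound decreases to 0.078 and the upper bound increases to 0.173.
3. For new cases, cite Table 4.4.2 and state that (0.007, 0.046) applies at an observed proportion of 2%.

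The interval, the direction and the table reference are the necessary corrections. The widths and percentages are advisable because they let the reader judge the choice of 250 directly.

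The cost is a few sentences in one section. The sample size, enrolment targets, both tables and the analysis stay as they are. The only substantive effect is that the stated precision for previously treated cases becomes slightly less favourable.
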